Appendix A: Schedule of Study Procedures

Study Period	Pre-Screen	Screen	Double-Blind					Open Label Extension										Post Treatment		
Study Week (from enrollment)	-8 to -2	-1	1	4	8	12	13	16	20	24	28	32	36	40	48	56	64	68	74	80
Study week (from start of open label extension)									4	8	12	16	20	24	32	40	48	52		
Inpatient Visits		x						x				x						x		x
Home Nurse visit**				x	x	x	x		x	x	x		x	x	x	x	x		x	
Telephone contact				x	x	x	x		x	x	x		x	x	x	x	x		x	
Inclusion/Exclusion Criteria	x	x																		
Medical History Review	x	x																		
Vital Signs/Weight/Height		x						x				x						x		x
Physical Exam		x						x				x						x		x
Waist Circumference		x						x				x						x		x
Skinfold measurements		x																		
DEXA Scan			x					x				x						x		
Glucose and Lipid Turnover			x					x				x						x		x
Euglycemic Hyperinsulinemic Clamp			x					x				x						x		x
Mixed Meal Test			x					x				x						x		x
Urinalysis & protein:creatinine ratio		x		x	x		x	x	x	x	x	x		x		x		x		x
Liver Biopsy			x															x		
MRI/MRS liver/heart			x					x				x						x		
Carotid intima-media thickness			x					x				x						x		
12-Lead EKG		x						x				x ¹						x		

7-point plasma glucose			X					X				X						X		X	
Weekly Study Drug SQ Injection			X	X	X	X	X	X	X	X	X	X	X	X	X	X	X	X	X		
Glucometer Dispensation/Training			X																		
Hunger Diary			X					X				X						X		X	
Widespread Pain Diary			X					X				X						X		X	
Quality of Life Assessments			X					X				X						X		X	
Review SMPG and Insulin Dose			X	X	X	X	X	X	X	X	X	X	X	X	X	X	X	X	X	X	X
Diet/Alcohol Counseling	---X---		X	X	X	X	X	X	X	X	X	X	X	X	X	X	X	X	X	X	X
Adverse Events			X	X	X	X	X	X	X	X	X	X	X	X	X	X	X	X	X	X	X
Concomitant Medication Review	X		X	X	X	X	X	X	X	X	X	X	X	X	X	X	X	X	X	X	X

¹ Patients previously treated with placebo, only

² One sample obtained on each of two consecutive days

³ Sampling schedule can be found in Appendix C.
 Unless specified, otherwise, PK and Antibodies will be collected predose.
 PK and immunogenicity testing does not need to be collected fasting.

* Platelets will be assessed every week

** Home Health Nurse Visits (or lab draw by local lab facility when needed) will take place every week unless patient will be at NIH for in-person visit.

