2.3.4 Clinical Experience

Detailed information concerning the clinical studies conducted with ISIS 304801 can be found in the ISIS 304801 Investigator’s Brochure. A summary is included below.

ISIS 304801 has been evaluated in one Phase 1 study and two Phase 2 studies, all double blinded and placebo controlled. The total exposures comprise 99 patients and healthy volunteers administered ISIS 304801 from 50 to 400 mg subcutaneously up to 3 months (compared to 37 administered placebo).

All clinical trials of ISIS 304801 have shown very large and clinically meaningful reductions in fasting apoC-III and TG (~80% and 70%, respectively, mean reduction from baseline with 300 mg dose) with a very high degree of consistency of response between the different patient groups. This includes healthy volunteers, patients with moderate to severe hypertriglyceridemia not on background TG-lowering therapy, patients with moderate to severe hypertriglyceridemia on a background of stable fibrate therapy, patients with Familial Chylomicronemia Syndrome (FCS), and patients with hypertriglyceridemia and T2DM. Comparison of the effects of ISIS 304801 at the 300 mg/week dose across several patient populations is shown in Table 2.

Table 2 Mean Percent Change from Baseline of Lipid Parameters in Hypertriglyceridemia Patients Treated with ISIS 304801 (300 mg/wk for 12 weeks) in Phase 2 Studies

Mean % (SD) Change from Baseline	Monotherapy in Hypertriglyceridemia and T2DM (N = 7) Mean Baseline TG 259 mg/dL	Monotherapy in Hypertriglyceridemia (N = 11) Mean Baseline TG 559 mg/dL	Add-on to Fibrate in Hypertriglyceridemia (N = 10) Mean Baseline TG 394 mg/dL
ApoC-III	-88% (6.0)*	-80% (9.3)***	-71% (13.0)**
Triglycerides	-72% (8.3)*	-71% (14.1)***	-64% (8.9)**
HDL-C	+40% (19.8)*	+46% (24.0)***	+52% (23.7)**

* p ≤ 0.05 vs. placebo

** p ≤ 0.01 vs. placebo

*** p ≤ 0.001 vs. placebo

In addition to the lipid analysis, the effect of lowering apoC-III on glycemic control and insulin sensitivity was evaluated in the subgroup of patients with hypertriglyceridemia and type 2 diabetes, by measuring

fructosamine, glycated albumin, and HbA1c and by performing a hyperinsulinemic euglycemic clamp at baseline and at the end of the treatment period.

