Statistically significant decreases were observed in the mean change from Baseline in % glycated albumin and in fructosamine 1 week after the last dose and in HbA1c and fructosamine at the end of the Follow-up Period (3 months after the last dose). These significant effects later in the Follow-up Period were likely a result of the long duration of response of ISIS 304801. Trends were also observed towards improvement in all measures of peripheral insulin sensitivity, but the small sample size of patients with valid clamps performed within the protocol-specified time window likely precluded statistical significance.

In clinical studies conducted to date, ISIS 304801 has been well tolerated and has shown a favorable safety profile. There has been no clinical or laboratory evidence of drug-drug interactions.

To date, there have been no ISIS 304801 associated laboratory abnormalities suggestive of an effect on the renal (serum creatinine, proteinuria) or hepatic systems (alanine aminotransferase [ALT], aspartate aminotransferase [AST], bilirubin) despite many patients in the Phase 2 clinical trials receiving concomitant medications that are known to be associated with elevations in hepatic enzymes, such as fibrates and statins. In Phase 2 studies, there was a mild decrease of platelet count associated with ISIS 304801 administration that recovered in the post-treatment period and was not associated with platelet-related adverse events (AEs).

The most frequently observed AEs with ISIS 304801 were local reactions at the injection site. Local cutaneous reactions at the injection site, defined as those events presenting as either pain, tenderness, erythema, pruritus or swelling occurring on the day of injection and persisting for at least 2 days (~15% of injections), were almost always mild, resolved spontaneously, were non-progressive, and were not associated with systemic sequelae.

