6.3.7 Post-Treatment

After completion of the open label extension (week 68), patients will enter the 12-week post-treatment evaluation period. This period consists of home platelet monitoring every week for six weeks and then again at a single NIH visit on week 80 as outlined in Appendix A.

Immediately after week 68, or after the post-treatment evaluation period, patients may choose to receive an additional 12 months of open label drug (up to 24 months, total). They will be offered this option if their triglycerides improved by $\geq 50\%$. Justification for this additional extension are:

- a. The patients received $\geq 50\%$ improvement in triglycerides and they have no other effective treatment options.
- b. To collect additional safety data over a longer term
- c. To collect additional efficacy data over a longer term

Home health care visits will not be available during the extended open-label period. Patients must obtain platelet and other safety monitoring locally through their health insurance provider or pay out of pocket. This monitoring will include weekly CBC for platelet count, and monthly CBC with differential, lipid panel, coagulation studies, urine protein:creatinine ratio, liver function tests, and chemistry panel. Hemoglobin A1c will be measured every 3 months. Study staff will remain in weekly contact with patients to review safety labs and any adverse events. Patients will return to NIH at the end of the 12 month extended open-label use period, or earlier if there are any safety concerns that, in the judgment of the PI, require in-person evaluation. During the NIH visit at the end of the 12 month period, patients may undergo optional evaluation including any test listed in section 6.4 except liver biopsy. All concomitant medications, including those for diabetes or hyperlipidemia, may be adjusted as clinically appropriate per the judgment of the investigator during the extended open-label period.

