6.4.5 Safety Assessments

1. Liver function, Kidney function, Platelets, LDL, and coagulation tests (detailed in Appendix B): Monitoring of the above (except for platelets) will be performed every 4 weeks for the first 6 months of treatment, and every 8 weeks thereafter, per the Study Schedule (Appendix A). Platelets will be monitored every week for the duration of the study.
2. Self-monitoring of blood glucose: In subjects with diabetes, a home glucometer will be distributed to patients who do not have one already at the first inpatient visit for home-based glucose monitoring (“Self-Monitored Plasma Glucose” or SMPG). Training on the use of the glucometer will be provided as needed. Fasting SMPG will be self-measured in the fasting state: daily if the patient is on insulin therapy, and weekly if on oral antidiabetic therapy.
3. Urinalysis: Urinalysis and urine protein to creatinine ratio will be conducted as per the Study Schedule (Appendix A).
4. Echocardiogram: Echocardiography for assessment of left and right ventricular function and mitral and aortic valve function will be conducted per the Study Schedule (Appendix A). Cardiologists reviewing echocardiograms at NIH will not be aware of treatment assignment during the randomized period. Results will be provided to the DSMB for their review.

5. **EKG:** Standard 12-lead EKGs will be performed after the patient has been resting in a supine position for at least 5 minutes per the Study Schedule (Appendix A).
6. **Troponin T:** Cardiac troponin T will be measured per the Study Schedule (Appendix A).
7. **Pregnancy test:** Pregnancy tests will be performed on female patients with reproductive potential at each inpatient visit.
8. **Pancreatitis:** All patients will be given an instruction card that must be presented to the treating physician if a suspected case of pancreatitis occurs. The card will explain that the patient is in a clinical trial and that serum lipase and/or amylase measures should be done in order to adjudicate the event, based on Atlanta Classification⁵¹. If serum or amylase activity is less than 3 x ULN, imaging, preferably contrast-enhanced computed tomography (CT), should be considered to confirm the diagnosis of acute pancreatitis per the Atlanta Criteria.

7. Human Subject Protection

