7.5.2 Safety Monitoring Rules for Renal Function

Patients with confirmed persistent changes that are observed over 2 consecutive visits, at least 7 days apart, for the criterion below should be retested every two weeks with serum creatinine and urine chemistries until creatinine and P/C ratio stabilize:

- P/C ratio change from baseline $> 50\%$ and ≥ 1.5 ULN

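### Between Weeks 32 and 68, on weekly drug, urinalysis and urine P/C are scheduled with nominal gaps of 8, 16 and 12 weeks; marking two existing home visits would cut the longest gap to 8 weeks

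*Combined protocol and SAP*

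**What the plan says.** Section 6.4.5, item 3, gives no interval of its own for urine: "Urinalysis and urine protein to creatinine ratio will be conducted as per the Study Schedule (Appendix A"). The timing therefore rests on one row of Appendix A, "Urinalysis & protein:creatinine ratio". That row is marked at Weeks -1, 4, 8, 13, 16, 20, 24, 28, 32, 40, 56, 68 and 80. Section 6.2.2.5 sets dosing once weekly through Week 68.

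Other parts of the protocol bear on the same question:

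- **Section 6.4.5, item 1.** Kidney function tests, with liver, LDL and coagulation tests, "will be performed every 4 weeks for the first 6 months of treatment, and every 8 weeks thereafter".
- **Section 6.3.7.** In the optional extra year, open to patients with at least 50% triglyceride lowering, local monitoring includes "monthly CBC with differential, lipid panel, coagulation studies, urine protein:creatinine ratio, liver function tests, and chemistry panel".
- **Section 7.5.2.** The only criterion is a "P/C ratio change from baseline" above 50% together with a value of at least 1.5 ULN, seen at two consecutive visits at least 7 days apart. Such patients "should be retested every two weeks with serum creatinine and urine chemistries until creatinine and P/C ratio stabilize".
- **Section 7.6.2.** Dosing may be paused for urine protein above 3.5 g/24 hours, or for a calculated creatinine clearance of 40 mL/min or less confirmed by a 24-hour collection.
- **Section 7.1.** The investigator reviews urinalysis, including dipstick protein, at least monthly.
- **Section 6.3.5 and Appendix A.** Home nurse visits are weekly, and Weeks 48 and 64 are among the visits with their own columns.

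**The concern.** After Week 40 the Appendix A columns run at 48, 56, 64 and 68. The urine row skips 48 and 64, and no reason is given. Urine is then tested less often than the other kidney labs, and less often than P/C will be tested in the following year for patients who stay on drug. The monthly review in Section 7.1 can go up to 16 weeks without a new scheduled urine result.

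What is at stake is how soon a rise in urine protein is seen. The Section 7.5.2 rule cannot start until a urine sample is taken, and serum creatinine does not measure urine protein. Section 2.1 names proteinuric nephropathy as a complication of the disease. Exclusion criterion 8e allows entry after positive protein dipsticks if, for example, the spot albumin:creatinine ratio is below 1000 mg/g. Section 2.3.4 reports that "there have been no ISIS 304801 associated laboratory abnormalities suggestive of an effect on the renal (serum creatinine, proteinuria") to date, but the people behind that statement were "administered ISIS 304801 from 50 to 400 mg subcutaneously up to 3 months". By Week 40 even a patient who began on placebo has had 40 - 16 = 24 weeks of active drug, so the 16-week gap lies beyond that experience for everyone.

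**Working it through.** **Inputs.** Urine marks, week columns and home-visit marks come from Appendix A. The 7-day confirmation interval is from Section 7.5.2, the visit window from Section 6.3.5, and the monthly P/C from Section 6.3.7. The header, urine row and home-visit row each have 20 cells and align.

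**1. The schedule as written**

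- Week 4 to Week 32: 7 intervals in 28 weeks, so 28/7 = 4.0 weeks per test.
- Week 32 to Week 68: gaps 40 - 32 = 8, 56 - 40 = 16, 68 - 56 = 12. Three tests in 36 weeks, so 36/3 = 12.0 weeks per test.
- Extended year: 12 tests in 52 weeks, so 52/12 = 4.3 weeks per test.

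**2. Relative rates**

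- Against the period to Week 32: (3/36)/(7/28) = 0.33.
- Against the extended year: (3/36)/(12/52) = 0.36.
- Against the off-drug Weeks 68-80: (3/36)/(1/12) = 1.0, so there is no difference.

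**3. The schedule with Weeks 48 and 64 added**

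- Tests at 32, 40, 48, 56, 64 and 68; gaps 8, 8, 8, 8 and 4. Five tests after Week 32, so 36/5 = 7.2 weeks per test.
- Week 48 alone leaves gaps of 8, 8, 8 and 12. Week 64 alone leaves 8, 16, 8 and 4. Both are needed to bring the maximum down to 8.

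**4. Gain in detection.** Assume a rise that crosses the threshold at once and persists, with visits on target.

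| Onset (weeks) | Width | First sample now | First sample with change | Gain (weeks) |
|---|---|---|---|---|
| 32-40 | 8 | 40 | 40 | 0 |
| 40-48 | 8 | 56 | 48 | 8 |
| 48-56 | 8 | 56 | 56 | 0 |
| 56-64 | 8 | 68 | 64 | 4 |
| 64-68 | 4 | 68 | 68 | 0 |

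With onset uniform over the 36 weeks, the mean gain is (8 x 8 + 8 x 4)/36 = 96/36 = 2.7 weeks. There is no gain for 8 + 8 + 4 = 20 of the 36 weeks.

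As a cross-check, the mean wait from onset to sample is the sum of squared gaps divided by 2 x 36:

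- Now: (64 + 256 + 144)/72 = 6.4 weeks.
- With the change: (4 x 64 + 16)/72 = 3.8 weeks.
- Before rounding, 464/72 - 272/72 = 192/72 = 2.7 weeks, which agrees.

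**5. When Section 7.5.2 can be met.** For a rise just after Week 40, with a second visit 7 days later, the earliest point is 56 + 1 = Week 57 now and 48 + 1 = Week 49 with the change.

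**6. Visit window.** If the two visits bounding a gap are each 7 days off target in opposite directions, a 16-week gap becomes 14 to 18 weeks and an 8-week gap 6 to 10 weeks. Section 6.3.5 gives 7 days as the least width of the window, so these are illustrations and not limits.

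**The case against.** The strongest reply is that this is a reasonable taper. The protocol also thins kidney labs and telephone contact as exposure grows, no renal signal has been reported, and the creatinine-clearance criterion in Section 7.6.2 operates throughout. Investigators can order extra tests. The average gain is under 3 weeks and more than half of onset times gain nothing. What is gained is earlier two-weekly retesting, since Section 7.5.2 does not stop dosing.

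Most of that is right, and it is why the point is minor. It does not remove the point. The taper for kidney labs is to 8 weeks, not 16. Creatinine clearance does not measure urine protein. The absence of a signal rests on at most 3 months of exposure.

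A reader might infer more than the documents support:

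- **That Appendix A breaches the protocol.** Section 7.1 sets how often results are reviewed, not how often urine is collected, and Section 6.4.5, item 3, leaves collection to Appendix A. The kidney tests of item 1 are set apart from urine, which has its own item.
- **That sampling is denser in everything that follows.** This is true only of the optional extension in Section 6.3.7, which lists P/C but not urinalysis. Off drug, Weeks 68-80 also have a 12-week gap.
- **That urine is the only laboratory mark missing at Weeks 48 and 64.** The laboratory rows of Appendix A are not in the text available here, so this cannot be confirmed.
- **That the change guarantees 8 weeks.** The figure is nominal, because the visit window has no stated upper limit.

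**Conclusion.** The concern holds as a minor monitoring gap. In Weeks 32-68 urine protein is scheduled 3 times in 36 weeks, about a third of the rate up to Week 32 and of the P/C rate in the optional extended year, and more sparsely than the protocol's other kidney labs. The longest nominal on-drug gap is 16 weeks, during which the only trigger of Section 7.5.2 has no new scheduled data.

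The schedule and gaps are read directly from Appendix A and need no assumption. The detection gains assume a persistent rise that crosses the threshold at once and visits on target; the 2.7-week average also assumes uniform onset. Nothing here shows that the drug harms the kidney or that a stopping decision would come sooner.

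**What to change.** In Appendix A, mark urinalysis and P/C at the home nurse visits of Weeks 48 and 64. The longest nominal on-drug gap then falls from 16 to 8 weeks, in line with the kidney labs of Section 6.4.5, item 1. This still does not give the monthly review in Section 7.1 a new urine result every month; it only halves the longest wait. If the sparser schedule is intended, one sentence in Section 6.4.5, item 3, should give the reason.

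The cost is two marks in one row and two extra urine samples per patient, or 2 x 10 = 20 samples for the planned 10 completers, with their handling. No visit is added. The downside is an occasional extra retest for a transient rise.

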Appendix B: List of Laboratory Analytes

Based on emerging data from this or future studies, additional tests not listed below may be performed on stored samples to better characterize the profile of ISIS 304801.

Clinical Chemistry Panel	Screening Tests	Hematology	Urinalysis

 • Sodium • Potassium • Chloride • Bicarbonate • Total protein • Albumin • Calcium • Magnesium • Phosphorus • BUN • Creatinine • Uric Acid • Total bilirubin • Direct (conjugated) bilirubin • Indirect (unconjugated) bilirubin • ALT • AST • Alkaline phosphatase 	
 • Hepatitis B surface antigen • Hepatitis C antibody • HIV antibody • FSH (women only) • Serum βhCG (women only) • TSH, T3, T4 
Coagulation
 
 • aPTT (sec) • PT (sec) • INR 
Lipid Panel
 
 • Total Cholesterol • LDL-C • HDL-C • Triglycerides • VLDL-C • Non-HDL-C • apoC-III (total, chylomicron, VLDL, LDL, HDL) 	
 • Red blood cells • Hemoglobin • Hematocrit • MCV, MCH, MCHC • Platelets • White blood cells • WBC Differential (% and absolute) • Neutrophils • Eosinophils • Basophils • Lymphocytes • Monocytes 
Pharmacokinetics & Immunogenicity
 
 • ISIS 304801 levels in plasma • Anti-ISIS 304801 antibodies in plasma 	
 • Color • Appearance • Specific gravity • pH • Protein • Blood • Ketones • Urobilinogen • Glucose • Bilirubin • Leukocyte esterase • Nitrate • Microscopic examination² 
Other assessments
 
 • hsCRP • Sedimentation Rate • C5a, Bb • HbA1c • Glucose • Insulin • C-peptide

- | | |
|---|---|
| 
• apoA-1• apoB• apoB-48• Lipoprotein particle size/number• Free fatty acids | 
• Troponin T• Adiponectin• Leptin• Testosterone (women only) |
|---|---|

- 1 Plasma PK samples may also be used for profiling of drug binding proteins, bioanalytical method validation purposes, stability assessments, metabolite assessments, immunogenicity testing (or possibly for purposes of immunogenicity assay development and/or validation), or to assess other actions of ISIS 304801 with plasma constituents
- 2 Will be performed on abnormal findings unless otherwise specified

Appendix C: PK Sampling Schedules

Blood PK Sampling Schedule: Week 16 (Week 1 OLE)

Week 16			
D1	D2	D3	D4
Predose, 1, 2, 3, 4, 6, 8, 12 hours post SC injection	24 hours	48 hours	72 hours

Blood PK Sampling Schedule: Week 32 (Month 4 OLE)

Week 32			
D1	D2	D3	D4
Predose, 1, 2, 3, 4, 6, 8, 12 hours post SC injection	24 hours	48 hours	72 hours

Appendix E: Financial Compensation

			Baseline admission		Week 16		Week 32		Week 68		Post-treatment	
Procedure	Inconvenience Units	Compensation	Count	Total	Count	Total	Count	Total	Count	Total	Count	Total
Inpatient stay	n/a	40	9	360	9	360	9	360	8	320	4	160
Home labs	1	10	0	0	15	150	15	150	34	340	4	40
7 point plasma glucose	3	30	1	30	1	30	1	30	1	30	1	30
DEXA	1	10	1	10	1	10	1	10	1	10	0	0
MRI	5	50	1	50	1	50	1	50	1	50		0
Mixed meal test	2	20	1	20	1	20	1	20	1	20	1	20
Euglycemic Clamp	5	50	1	50	1	50	1	50	1	50	1	50
Liver Biopsy	5	50	1	50	1	50	0	0	0	0	0	0
Study diaries	1	10	1	10	1	10	1	10	1	10	1	10
Visit completion bonus					250		250		250		250	
Total					580		980		1080		560	

Grand total 4130

Appendix F: EQ-5D-5L Health Questionnaire (English and Spanish versions)

Health Questionnaire

English version for the USA

USA (English) © 2009 EuroQoL Group EQ-5D™ is a trade mark of the EuroQoL Group

Under each heading, please check the ONE box that best describes your health TODAY.

MOBILITY

- I have no problems walking
- I have slight problems walking
- I have moderate problems walking
- I have severe problems walking
- I am unable to walk

SELF-CARE

- I have no problems washing or dressing myself
- I have slight problems washing or dressing myself
- I have moderate problems washing or dressing myself
- I have severe problems washing or dressing myself
- I am unable to wash or dress myself

USUAL ACTIVITIES (e.g. work, study, housework, family or leisure activities)

- I have no problems doing my usual activities
- I have slight problems doing my usual activities
- I have moderate problems doing my usual activities
- I have severe problems doing my usual activities
- I am unable to do my usual activities

PAIN / DISCOMFORT

[figure not shown]
- I have no pain or discomfort
- I have slight pain or discomfort
- I have moderate pain or discomfort
- I have severe pain or discomfort
- I have extreme pain or discomfort

ANXIETY / DEPRESSION

- I am not anxious or depressed
- I am slightly anxious or depressed
- I am moderately anxious or depressed
- I am severely anxious or depressed
- I am extremely anxious or depressed

- We would like to know how good or bad your health is TODAY.
- This scale is numbered from 0 to 100.
- 100 means the best health you can imagine.
0 means the worst health you can imagine.
- Mark an X on the scale to indicate how your health is TODAY.
- Now, please write the number you marked on the scale in the box below.

YOUR HEALTH TODAY =

Cuestionario de Salud

Versión en español para los EE. UU.

(Spanish version for the USA)

USA (Spanish) © 2009 EuroQol Group EQ-5D™ is a trade mark of the EuroQol Group

Debajo de cada encabezamiento, marque UNA casilla, la que mejor describe su salud HOY.

MOVILIDAD

- No tengo problemas para caminar
- Tengo problemas leves para caminar
- Tengo problemas moderados para caminar
- Tengo problemas graves para caminar
- No puedo caminar

CUIDADO PERSONAL

- No tengo problemas para lavarme o vestirme solo/a
- Tengo problemas leves para lavarme o vestirme solo/a
- Tengo problemas moderados para lavarme o vestirme solo/a
- Tengo problemas graves para lavarme o vestirme solo/a
- No puedo lavarme o vestirme solo/a

ACTIVIDADES DE TODOS LOS DÍAS (Ej.: trabajar, estudiar, hacer las tareas domésticas, actividades familiares o actividades de ocio)

- No tengo problemas para realizar mis actividades de todos los días
- Tengo problemas leves para realizar mis actividades de todos los días
- Tengo problemas moderados para realizar mis actividades de todos los días
- Tengo problemas graves para realizar mis actividades de todos los días
- No puedo realizar mis actividades de todos los días

DOLOR / MALESTAR

[figure not shown]
- No tengo dolor ni malestar
- Tengo dolor o malestar leve
- Tengo dolor o malestar moderado
- Tengo dolor o malestar intenso
- Tengo dolor o malestar extremo

ANSIEDAD / DEPRESIÓN

- No estoy ansioso/a ni deprimido/a
- Estoy levemente ansioso/a o deprimido/a
- Estoy moderadamente ansioso/a o deprimido/a
- Estoy muy ansioso/a o deprimido/a
- Estoy extremadamente ansioso/a o deprimido/a

- Nos gustaría saber lo buena o mala que es su salud HOY.
- La escala está numerada de 0 a 100.
- 100 representa la mejor salud que se pueda imaginar.
0 representa la peor salud que se pueda imaginar.
- Por favor haga una X en la escala para indicar cuál es su estado de salud HOY.
- Ahora, por favor escriba en la casilla que encontrará a continuación el número que ha marcado en la escala.

SU SALUD HOY =

